#### **4.3 Subject Disposition**

The subject dispositions will be presented. Number and percentages of subjects will be presented who are:

- Enrolled
- ITT
- Per protocol (PP)

Site breakdown table will be given for Enrolled, ITT, and per protocol analysis sets.

#### **4.4 PCL characteristics**

PCL characteristics will be summarized. PCL characteristic include location of cystic lesion, morphology, connection to pancreatic duct, solid components, presence of visible mucin, distinct PCL wall and mural nodule.

#### **4.5 Control of Systematic Error**

Stratified randomization of needle types (with PCL Location strata) will be done to control for selection bias.

#### **4.6 Number of Subjects per Investigative Site**

A total of 250 subjects will be enrolled in this trial at 7 to 12 investigational sites. To avoid that enrollment be too heavily biased towards one site, an enrollment maximum by site will be instituted per clinical study agreement between each investigational site and the Sponsor.

#### **4.7 Methods for Handling Missing Data**

As per section 5.6, in fitting a multivariate model, if there are missing categorical covariates in the model, an appropriate statistical method (for example, for generalized linear model, Ibrahim (1990, JASA)) will be used. For missing values related to dates see section 7.4.

In the other data analysis (for example missing continuous covariates), the adjustments for missing data will be performed only if deemed necessary and will be described completely. In all such situations, a sensitivity analysis will be performed to justify all adjustments.

### **5 ADDITIONAL DATA ANALYSES**

#### **5.1 Other Endpoints/Measurements**

##### **5.1.1 Secondary Endpoints**

Secondary endpoints are listed below. These endpoints will be summarized based on ITT and per protocol (PP) population using descriptive statistics (mean, standard deviation, n, minimum, maximum) for continuous variables and frequency statistics for discrete

variables. For a sample table based on ITT population or per protocol population see the appendix.

### Safety Endpoint

- Occurrence, severity and relatedness of adverse events to the needle and procedure

### Other Endpoints

- Extent of cyst aspiration as measured by reduction of maximal cyst diameter before and after FNA (converted to volume by standard geometric formulation)
- Successful echoendoscopic fine needle aspiration of PCL, defined as complete cyst aspiration or collection of aspirate adequate to perform two standard assays: cytology and carcinoembryonic antigen (CEA)
- Ability to reach and penetrate the PCL, stratified by route of access and PCL location
- Number of EUS-FNA needles and EUS-FNA needle passes used
- Time needed for aspiration for each pass and time from first needle pass in to last needle pass out
- Ease of needle passage in and out of echoendoscope and quality of needle visualization inside the cyst, categorized as *Excellent, Very Good, Good, Fair, and Poor*
- Accuracy of two EUS-FNA-based standard assays (cytology and CEA) as a diagnostic measure of disease state categorized as one of the following: *serous cyst, mucinous cyst, intra papillary mucinous neoplasm (IPMN), or pseudocyst*
- Post EUS-FNA patient management plan (clinical and/or imaging surveillance, percutaneous aspiration, surgical removal)
- Impact of EUS-FNA based assays on diagnosis
- Rate of cross-over to salvage arm

#### 5.1.2 Diagnostic Accuracy Measures

Diagnostic accuracy is defined in terms of “disease state” and the following three disease state categories will be used in this study in order to assess diagnostic accuracy of EUS-FNA:

- “*Disease State per EUS-FNA*”: This measure is derived from the results of the cytology and chemistry assays of the cyst aspirate. Cysts will be classified as *serous cyst, mucinous cyst, IPMN, or pseudocyst* based on the table below. If any of the aspirate assays are not performed or the results from the two aspirate-based assays do not follow the table below, then the Disease State per EUS-FNA will be classified as

*Indeterminate.* The Disease State per EUS-FNA will be recorded on the *Cytology and Chemistry Results CRF*.

Disease State per EUS-FNA	Cytology	Cyst Fluid CEA (ng/mL)
Serous	Bland PAS +*	< 0.5
Mucinous	Mucinous	> 200
IPMN	Mucinous	> 200
Pseudocyst	Pigmented histiocytes	< 200

\* This cytological assay might be replaced by another cytological assay as needed

In order to assess the accuracy of EUS-FNA-based standard assays (cytology and CEA) as a diagnostic measure of disease state, the *Disease State per EUS-FNA* measure will be compared to a reference diagnosis. The reference diagnostic standard will be diagnosis from a surgical specimen histology, the true gold standard for cases that evolve to surgical resection within the 30 day follow-up time of the protocol. For cases that do not progress to surgery within 30 days of the EUS-FNA procedure, the reference diagnostic standard will be a composite diagnosis by a consensus board. The consensus board will consist of 3 to 5 Investigators who will be blinded to the type of needle used. The diagnosis of disease state will be based solely on baseline medical history and EUS and cross sectional imaging of the cyst. Information regarding aspirate characteristics and results from aspirate tests will not be provided to the consensus board. Diagnoses will be rendered at a separate Investigators Meeting or virtual meeting.

- “*Disease State per Histology*”: This is the reference diagnostic standard. This measure is derived from the histology results of the surgical specimen in cases that progress to surgery within 30 days. Cysts will be classified as follows: *serous cyst*, *mucinous cyst*, *IPMN*, *pseudocyst*, or *Indeterminate*. As described above, this measure will serve as the gold standard for assessing diagnostic accuracy.
- “*Disease State per Consensus Board*”: This is the surrogate for the reference diagnostic standard. This measure is derived by the consensus board as described above. Cysts will be classified as follows: *serous cyst*, *mucinous cyst*, *IPMN*, *pseudocyst*, or *Indeterminate*. The classification will be based on baseline medical history and EUS and cross sectional imaging. Medical history will include, but not be limited to presence or absence of prior necrotizing pancreatitis, trauma or other potential cause of pseudocyst. Imaging will pertain to cyst location and cyst appearance.

**Degree of correlation between *Disease State per EUS-FNA* and *Disease State per Consensus Board or per Histology*** is illustrated below.

Total number of subjects enrolled is sum of all entries, namely

$$\text{TOTAL} = A + B + C + \dots + S + T + U + V + W + X + Y.$$

PCL Type	Serous per Consensus Board or Histology	Mucinous per Consensus Board or Histology	IPMN per Consensus Board or Histology	Pseudocyst Per Consensus Board or Histology	Indeterminate per Consensus Board or Histology
Serous per EUS-FNA	A	E	F	G	U
Mucinous per EUS-FNA	K	B	H	I	V
IPMN per EUS-FNA	L	M	C	J	W
Pseudocyst Per EUS-FNA	N	O	P	D	X
Indeterminate Per EUS-FNA	Q	R	S	T	Y

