- h. Accuracy of two EUS-FNA-based standard assays (cytology and CEA) as a diagnostic measure of disease state categorized as one of the following: *serous cyst, mucinous cyst, intra papillary mucinous neoplasm (IPMN), or pseudocyst*.

NOTES:

- Determination of disease state per EUS-FNA will be based on results from cytology and CEA and will follow published criteria.⁴ Definitions of the diagnostic accuracy measures are provided in **Appendix C.3**.
- Samples that do not have both diagnostic assay results (cytology and CEA) will be labeled as *Indeterminate*.

- i. Post EUS-FNA patient management plan (clinical and/or imaging surveillance, percutaneous aspiration, surgical removal).
- j. Impact of EUS-FNA based assays on diagnosis.
- k. Rate of cross-over to salvage.

5. Subject Selection

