8.3. Procedure

8.3.1. Lesion Characteristics

The following lesion characteristics will be assessed by EUS prior to the start of the FNA procedure and will be recorded on the *Procedure CRF*:

- a. Cyst size (maximal diameter, and cross-sectional diameter)

NOTE: In the case of a multilocular cyst, size will be measured both as the aggregate size of all cyst locules and the long and short perpendicular axis of the largest locule.

- b. Number of locules (1, 2, 3, 4, 5, 6-10, > 10)
- c. Presence of visible mucin (floating, or mobile filling defects)
- d. Presence of mural nodule (non-mobile filling defect) and size
- e. Presence of solid components
- f. Presence of distinct PCL wall
- g. Connectivity to pancreatic duct
- h. Maximal pancreatic duct diameter

An EUS image of the patient's PCL will be saved during the procedure.

8.3.2. *EUS-FNA Procedure*

The EUS-FNA procedure will be carried out in line with the guidelines provided in **Section 7** above, and the following data will be collected and recorded on the *Procedure CRF*:

- a. Route of access (gastric, duodenal, esophageal)
- b. Ease of insertion of EUS-FNA needle through echoendoscope
- c. Ability to reach target lesion
- d. Ability to penetrate into target lesion
- e. Quality of needle visualization
- f. Number of needle passes
- g. Ease of removal of EUS-FNA needle from echoendoscope
- h. Aspirate characteristics and adequacy of aspirate volume to perform two assays (cytology and CEA)
- i. Adverse Event assessment during procedure and through 2 Hours Post-Procedure or discharge from endoscopy unit

8.4. **Cytology and Chemistry Results**

The results of cyst aspirate cytology and CEA assessments will be provided by the cytology and chemistry labs and will be recorded on the *Cytology and Chemistry Results CRF*. Results will be categorized as follows⁴ and will be used for determination of Disease State per EUS-FNA:

- Cytology
 - Bland PAS +
 - Mucinous
 - Pigmented histiocytes
- CEA (ng/mL)
 - < 0.5
 - > 0.5 and < 200
 - > 200

8.5. **30-Day Follow-up**

The post-procedure 30-day Follow-up Visit will be conducted over the telephone. The visit window allows for this visit to occur anytime from 25 days to 35 days post procedure. Patients will be assessed for potential adverse events that might have occurred from discharge until 30 days post-procedure. AE information will be recorded on the *Adverse Event CRF*.

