12 AUG 2016

FINAL

Boston Scientific

Randomized Evaluation of PCLs Using Three EUS-FNA Needles

90869947 Rev/Ver. AG

Page 41 of 46

Design Parameters:

One-sided Type I Error=0.05

Multiple comparison procedure= Hochberg's step up

Total Sample required=100

Rejection region=Right tail

Treatment parameters:

Arm	Mean volume ratio	Standard Deviation	Sample size per group
22G	67	15.29	25
19G	77	4.67	25
19GFlex	77	4.67	50

Overall:

Global (reject any H_i): 0.912

Conjunctive (reject all H_i): 0.901

Secondary endpoint c) considerations:

It is the desire of this study to demonstrate superiority of the EUS-FNA 19 G Flex needle over two other needles:

- One offering the same needle diameter, but without added needle flexibility, namely the standard 19 G needle
- One offering better needle flexibility via a reduced needle diameter, namely the standard 22 G needle

Superiority by 16% or more is deemed clinically significant. Statistical power of 80% is chosen using the multiple comparison Hochberg's method. Test results are shown below, resulting in the requirement for 121 patients for 19 G Flex arm and 61 patients each for 19 G and 22G arm.

Hypothesis:

$H_i: \pi_i - \pi_0 \leq 0$ Versus $K_i: \pi_i - \pi_0 >$ for $i=1,2$

Design Parameters:

One-sided Type I Error=0.05

Multiple comparison procedure= Hochberg's step up

Total Sample required=243

Rejection region=Right tail

Treatment Parameters:

Arm	Response rate	Sample size per group
19GFlex	0.91	121
19G	0.75	61
22G	0.75	61

Overall:

Global (reject any H_i): 0.947

Conjunctive (reject all H_i): 0.808

C.3 Diagnostic Accuracy Measures

Diagnostic accuracy is defined in terms of “disease state” and the following three disease state categories will be used in this study in order to assess diagnostic accuracy of EUS-FNA:

- “*Disease State per EUS-FNA*”: This measure is derived from the results of the cytology and chemistry assays of the cyst aspirate. Cysts will be classified as *serous cyst*, *mucinous cyst*, *IPMN*, or *pseudocyst* based on the table below.⁴ If any of the aspirate assays are not performed or the results from the two aspirate-based assays do not follow the table below, then the Disease State per EUS-FNA will be classified as *Indeterminate*. The Disease State per EUS-FNA will be recorded on the *Cytology and Chemistry Results CRF*.

Disease State per EUS-FNA	Cytology	Cyst Fluid CEA (ng/mL)
Serous	Bland PAS +*	< 0.5
Mucinous	Mucinous	> 200
IPMN	Mucinous	> 200

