## 1 PROTOCOL SUMMARY

[figure not shown]
Primary Objective	To document impact of EUS-FNA needle gauge and flexibility on effectiveness of pancreatic cystic lesions (PCL) aspiration, on ability to obtain sufficient material for standard diagnostic testing, and on diagnostic accuracy of EUS-FNA aspirate for differentiation of mucinous (pre-malignant) and non-mucinous cysts.
Devices	
Name Expect™ Endoscopic Ultrasound Aspiration Needle
 
Cleared Indication The Expect™ Needle is designed to sample targeted sub mucosal and extramural gastrointestinal lesions through the accessory channel of a curvilinear echoendoscope.
 
Device Categories
 
 
• Expect 22 gauge (22 G)
 
• Expect 19 gauge (19 G)
 
• Expect 19 gauge Flex (19 G Flex)
 

Study Design	
Prospective, multi-center study
 
Three arm randomized (19 G Flex, 22 G, 19 G) in 2:1:1 ratio with salvage. Salvage procedure will use 19 G Flex for subjects originally randomized to 19 G or 22 G standard needles, and will use 19 G or 22 G standard needle at investigator discretion for subjects originally randomized to 19 G Flex needle.
 
Phased
 
 
• Phase I: 2 centers
 
• Phase II: expanded to 7 to 12 centers
 

Number of Subjects	250 subjects (121 in 19 G Flex arm, and 61 subjects each in 22 G and 19G arm, rounded up) 30 out of the 250 subjects will be enrolled in Phase I, and 220 subjects will be enrolled in Phase II.
Number of Centers	7 to 12 centers
Primary Endpoint	Volume of aspirated cyst fluid as a function of estimated maximal volume based on pre-aspiration EUS measure of cyst diameter (s) (%)

	aspiration of total estimated volume)

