#### Diagnostic accuracy for Mucinous Cysts:

- Sensitivity  

$$= [B] / [B+M+O+E+R]$$
- Specificity  

$$= [A+C+D+Y+F+G+J+L+N+P+Q+S+T+U+W+X] / [A+C+D+F+G+H+I+J+K+L+N+P+Q+S+T+U+W+X+Y+V]$$
- Positive Predictive Value (PPV)  

$$= [B] / [B+H+I+K+V]$$
- Negative Predictive Value (NPV)  

$$= [A+C+D+F+G+J+L+N+P+Q+S+T+Y+U+W+X] / [A+C+D+E+F+G+J+L+M+N+O+P+Q+R+S+T+U+W+X+Y]$$
- Overall Accuracy  

$$= [A+B+C+D+F+G+J+L+N+P+Q+S+T+U+W+X+Y] / TOTAL$$

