#### Diagnostic accuracy for IPMN:

- Sensitivity  

$$= [C] / [C+F+H+P+S]$$
- Specificity  

$$= [A+B+D+E+G+I+K+N+O+Q+R+T+U+V+W+X+Y] / [A+B+D+E+G+I+J+K+L+M+N+O+Q+R+T+U+V+W+X+Y+W]$$
- Positive Predictive Value (PPV)  

$$= [C] / [C+J+L+M+W]$$
- Negative Predictive Value (NPV)  

$$= [A+B+D+E+G+I+K+N+O+Q+R+T+U+V+W+X+Y] / [A+B+D+E+F+G+H+I+K+N+O+P+Q+R+S+T+U+V+W+X+Y]$$
- Overall Accuracy  

$$= [A+B+C+D+E+G+I+K+N+O+Q+R+T+U+V+W+X+Y] / TOTAL$$

**Diagnostic accuracy for Pseudocysts (in principle excluded from study, but a few cases may not have been identified at baseline as such):**

- Sensitivity  
=  $[D] / [D+G+I+J+T]$
- Specificity  
=  $[A+B+C+E+F+H+K+L+M+Q+R+S+U+V+W+Y] / [A+B+C+E+F+H+K+L+M+N+O+P+Q+R+S+U+V+W+Y+X]$
- Positive Predictive Value (PPV)  
=  $[D] / [D+N+O+P+X]$
- Negative Predictive Value (NPV)  
=  $[A+B+C+E+F+H+K+L+M+Q+R+S+U+V+W+Y] / [A+B+C+E+F+G+H+I+J+K+L+M+Q+R+S+T+U+V+W+Y+X]$
- Overall Accuracy  
=  $[A+B+C+D+E+F+H+K+L+M+Q+R+S+U+V+W+Y] / \text{TOTAL}$

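### The two aspirate assays cannot separate Mucinous from IPMN, no formula pools them for the objective's mucinous versus non-mucinous contrast, and the pseudocyst NPV denominator wrongly includes cell X

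*SAP*

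**What the plan says.** **Index test.** Both documents derive the EUS-FNA class from cytology and CEA. SAP 5.1.2: "This measure is derived from the results of the cytology and chemistry assays of the cyst aspirate". Protocol 4.2, note to endpoint h: "Determination of disease state per EUS-FNA will be based on results from cytology and CEA and will follow published criteria". In the classification table of both documents the Mucinous and IPMN rows carry the same entries: mucinous cytology, CEA above 200 ng/mL. A sample is Indeterminate under this condition (protocol C.3): "If any of the aspirate assays are not performed or the results from the two aspirate-based assays do not follow the table below".

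**Reference.** Histology is used if surgery follows within 30 days. Otherwise a consensus board gives a diagnosis "based solely on baseline medical history and EUS and cross sectional imaging of the cyst".

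**Objective.** The primary objective has three parts. The third is "diagnostic accuracy of EUS-FNA aspirate for differentiation of mucinous (pre-malignant) and non-mucinous cysts".

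**Formulas.** A 5x5 table with cells A to Y crosses EUS-FNA class (rows) with reference class (columns). Sensitivity, specificity, PPV, NPV and accuracy follow for each of four classes, one versus the rest. Two strings matter here:
- Mucinous specificity numerator: "A+C+D+Y+F+G+J+L+N+P+Q+S+T+U+W+X"
- Pseudocyst NPV denominator: "A+B+C+E+F+G+H+I+J+K+L+M+Q+R+S+T+U+V+W+Y+X"

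Overall agreement is [A+B+C+D+Y] / TOTAL. SAP 5.1.1 summarises endpoint h with descriptive statistics only.

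**The concern.** Two rows of the accuracy table share one entry rule. Something other than the stated test must place a cyst in one row or the other, so the class-specific results partly reflect an unstated decision. A reader looking for the objective's contrast will also turn to the measures headed Mucinous, and those score IPMN as not mucinous. The contrast can be summed from the planned table. But protocol 9.3 labels additional analyses as ad hoc, so a grouping chosen later would carry that label and would be open to choice after the data are seen.

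The NPV point is a slip in one formula, repeated in both documents.

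**Working it through.** **1. Can anything stated separate the two rows?** The table does not. The published-criteria note in protocol 4.2 does not either, because it also rests on cytology and CEA. Protocol 8.3.1 records "Connectivity to pancreatic duct" at EUS, but this is not an input to the class. If it were used, the measure would no longer rest on the assays alone and would share EUS imaging with the consensus-board reference.

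**2. Set check of the formulas.** The table is:

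| EUS-FNA \ reference | Serous | Mucinous | IPMN | Pseudocyst | Indet. |
|---|---|---|---|---|---|
| Serous | A | E | F | G | U |
| Mucinous | K | B | H | I | V |
| IPMN | L | M | C | J | W |
| Pseudocyst | N | O | P | D | X |
| Indet. | Q | R | S | T | Y |

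For each class, TP is the diagonal cell, FP the rest of its row, FN the rest of its column and TN everything else. Comparing 4 classes x 5 measures = 20 formulas per document:
- **Protocol:** 19 of 20 match. The exception is pseudocyst NPV. Test negatives are 25 - 5 = 20 cells; the stated denominator has 21, the extra one being X. X is already in the pseudocyst PPV denominator, D+N+O+P+X, so the two denominators sum to TOTAL + X. The protocol's other three NPV denominators omit the matching cell (U, V and W).
- **SAP, as read:** the same X error. In addition, IPMN specificity and NPV (numerator and denominator) and accuracy (numerator) each carry a W that the protocol's versions do not.

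The Mucinous formulas are correct one-versus-rest sums. In them M is a miss, H a false positive and C a true negative.

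**3. Pooled cells.** Group Mucinous with IPMN, use cysts with a determinate reference, and count FNA-indeterminates as test-negative:
- TP = B+C+H+M
- FP = I+J+K+L
- FN = E+F+O+P+R+S
- TN = A+D+G+N+Q+T

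That is 4 + 4 + 6 + 6 = 20 cells, each used once. The other five are U, V, W, X and Y.

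**4. Size of the split effect (all counts assumed).** Take 60 reference Mucinous, 60 reference IPMN and 80 others. The shared rule is met by 80% of the 120 (96) and 10% of the 80 (8). A share f of these is coded Mucinous regardless of truth, which is a worst case.

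| | f = 0.5 | f = 0.75 |
|---|---|---|
| Mucinous sensitivity | 24/60 = 40% | 36/60 = 60% |
| IPMN sensitivity | 24/60 = 40% | 12/60 = 20% |
| Mucinous specificity | 112/140 = 80% | 98/140 = 70% |
| Mucinous PPV | 24/52 = 46.2% | 36/78 = 46.2% |
| Pooled sensitivity | 96/120 = 80% | 96/120 = 80% |
| Pooled specificity | 72/80 = 90% | 72/80 = 90% |

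Mucinous PPV does not move with f. It equals 48/104, the share of reference Mucinous cysts among all that meet the rule, so it too says nothing about telling the two classes apart.

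**5. Indeterminates.** The 24 misses need not be Serous or Pseudocyst. Mucinous cytology with CEA not above 200 fits no row and becomes Indeterminate. If all 24 go that way, pooled sensitivity is 96/120 = 80% with indeterminates as test-negative, but 96/96 = 100% among determinate results only.

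**6. Size of the X effect (assumed TN = 220, FN = 5, X = 2).** Correct NPV is 220/225 = 97.8%. As written it is 220/227 = 96.9%.

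**The case against.** **Endpoint h keeps mucinous cyst and IPMN as separate classes, and neither document says IPMN belongs with mucinous in the objective.** This stands. The IPMN name and its mucinous cytology row support pooling, but pooling remains an assumption. A reader might infer that the Mucinous formulas are miscalculated. They are not; they answer a different question.

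**The planned table already allows any collapse.** This also stands. A reader might infer that the objective's contrast cannot be estimated, but only the stated formula and grouping are missing.

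**Counting Y as agreement looks like an error.** The documents do not support that reading. Indeterminate is a defined class on both sides, so crediting concordance is a choice. It does credit two non-diagnoses. With an assumed 200 reference-determinate cysts, 100 of them agreeing, and 50 reference-indeterminate, the written formula gives (100+50)/250 = 60% if FNA is indeterminate in all 50, and 100/250 = 40% if it is determinate in all 50.

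**The extra W might be read as a further SAP error.** It may come from reading the PDF text and cannot carry weight until the source is checked.

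**The practical effect is limited.** Endpoint h is not tested, and known pseudocysts are excluded, so X should be small. This bears on priority, not on whether the rules are wrong as written.

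**Conclusion.** The concern holds in three parts. First, Mucinous and IPMN share one assay rule in both documents, so the split between their rows, and the sensitivity, specificity and PPV built on it, cannot be interpreted as performance of the assays. Second, no stated formula gives the mucinous versus non-mucinous contrast named in the third part of the primary objective. Third, X does not belong in the pseudocyst NPV denominator.

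The split can move class sensitivity by 20 points between f = 0.5 and f = 0.75 while the pooled figure does not change. That size rests on assumed counts and on coding regardless of truth. The X effect is 0.9 points in the example and zero if X = 0. A reader might infer a threat to the trial's main conclusions, but the primary endpoint and endpoint c do not use these formulas. The point should be corrected before the accuracy results are reported.

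**What to change.** (a) State that IPMN is grouped with Mucinous for the objective's contrast. Add the pooled 2x2 table of step 3, by arm. Make the version with FNA-indeterminates as test-negative the main one; this is how the documents' own formulas treat the indeterminate row. Leaving out reference-indeterminate cysts departs from those formulas, so report the counts in U, V, W, X and Y. Give the version without Q, R, S and T as supportive, with the FNA-indeterminate rate by arm. Both are needed, since they can differ as much as 80% and 100%.

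(b) Keep the four-class table as descriptive, and state that its Mucinous/IPMN split cannot be interpreted from the assays.

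(c) Delete X from the pseudocyst NPV denominator in both documents. Check the W strings in the SAP's IPMN formulas against the source PDF. If the extra W is real, use the protocol's formulas.

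(d) Optional: beside the planned agreement figure, report [A+B+C+D] / [TOTAL - (U+V+W+X+Y)]. In the example under the objection this is 100/200 = 50% in both cases.

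**Cost.** Wording in SAP 5.1.2 and protocol C.3, and some programming; no new data. The protocol text may need an amendment with EC/IRB approval under Appendix B.2. If the plan is already in place, the change must be labelled ad hoc under protocol 9.3.

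### The accuracy tables pool surgical histology and a history-and-imaging consensus board into one set of reference columns, with no analysis by reference source

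*SAP*

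**What the plan says.** SAP 5.1.2 sets up a two-level reference for judging the aspirate assays (cytology and CEA). Histology is "the true gold standard for cases that evolve to surgical resection within the 30 day follow-up time of the protocol". For all other patients, "the reference diagnostic standard will be a composite diagnosis by a consensus board". The plan ranks the two. Of histology it says "this measure will serve as the gold standard for assessing diagnostic accuracy"; of the board diagnosis it says "This is the surrogate for the reference diagnostic standard".

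On what the board sees, the SAP says "The diagnosis of disease state will be based solely on baseline medical history and EUS and cross sectional imaging of the cyst". Its members are investigators "who will be blinded to the type of needle used", and aspirate characteristics and results are withheld from them.

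One 5x5 table follows, with cells A to Y. Its rows are the aspirate-based disease state. Its columns are the reference disease state with both sources merged, as in "Mucinous per Consensus Board or Histology". Above the table the SAP states: "Total number of subjects enrolled is sum of all entries". Protocol Appendix C.3 has the same reference definitions and the same table.

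**The concern.** The plan distinguishes a stronger from a weaker reference and then drops the distinction in the analysis. When aspirate and board disagree, the board may be the one in error, but the disagreement counts against the aspirate. When both make the same mistake, it counts in the aspirate's favour. A reader of the pooled table cannot tell how much of either is present.

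Assignment to a reference is also not random. The Protocol's Introduction expects better diagnostic yield to help treatment decisions, and endpoints i and j record the post-procedure management plan (surgical removal included) and the effect of the assays on diagnosis. It is therefore plausible that the aspirate result helps determine who is resected within 30 days, so that the reference a patient receives depends on the test being judged.

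At stake is the meaning of endpoint h and of the diagnostic-accuracy part of the primary objective. A number reported as accuracy could lie well away from accuracy against tissue.

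**Working it through.** **1. Can the planned formulas separate the two sources?** The SAP's sensitivity denominators, set against the table columns:

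- Serous: A+K+L+N+Q, the full merged serous column.
- Mucinous: B+M+O+E+R, the full merged mucinous column.
- IPMN: C+F+H+P+S, the full merged IPMN column.
- Pseudocyst: D+G+I+J+T, the full merged pseudocyst column.

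Overall agreement is (A+B+C+D+Y)/TOTAL, with TOTAL equal to all enrolled. No cell records the reference source, so no formula can recover it. The word *or* in the column heads might suggest a template for two tables, but cells that sum to all enrolled subjects rule that out.

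**2. Is the split made elsewhere?** SAP 5.3 names gender as the only subgroup and otherwise leaves room for unspecified further analyses. SAP 5.1.1 summarises secondary endpoints descriptively. No table by reference source, board-versus-histology comparison or sensitivity analysis is specified for endpoint h.

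**3. How far could the pooled figure move?** The documents give no expected assay accuracy, board accuracy or 30-day resection rate, so there is no plan figure to reproduce and every rate below is an assumption. The illustration is binary (mucinous or not), with assay accuracy a = 0.85, board accuracy b = 0.75, resected share f = 0.15, and resection unrelated to whether the assay is right.

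- Agreement with the board, independent errors: ab + (1−a)(1−b) = 0.85×0.75 + 0.15×0.25 = 0.675.
- Pooled: f×a + (1−f)×agreement = 0.15×0.85 + 0.85×0.675 = 0.701.
- With b = 0.65, agreement is 0.605 and pooled accuracy 0.642. With b = 0.95, agreement is 0.815 and pooled accuracy 0.820.
- Fully shared errors (the board is wrong whenever the assay is wrong), b = 0.75: agreement = 0.75 both right + 0.15 both wrong = 0.90; pooled = 0.15×0.85 + 0.85×0.90 = 0.893.

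A true 85% can therefore read as 70% or as 89% at the same board accuracy, depending only on how the errors are related.

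**4. Sensitivity and specificity.** Assume true values of 0.70 and 0.90, prevalence 0.5, board sensitivity and specificity 0.8, 10% resected and independent errors. The probability of a positive reference is q1 = 0.1 + 0.9×0.8 = 0.82 in mucinous cysts and q0 = 0.9×0.2 = 0.18 in the others.

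- Apparent sensitivity = (0.5×0.70×0.82 + 0.5×0.10×0.18)/(0.5×0.82 + 0.5×0.18) = 0.592.
- Apparent specificity = (0.5×0.30×0.18 + 0.5×0.90×0.82)/0.5 = 0.792.

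**5. Would histology alone be clean?** Not if the aspirate result drives resection. Assume sensitivity and specificity 0.85, prevalence 0.5, and resection of 30% of assay-positives and 5% of assay-negatives.

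- Raw sensitivity = (0.85×0.30)/(0.85×0.30 + 0.15×0.05) = 0.255/0.2625 = 0.97.
- Raw specificity = (0.85×0.05)/(0.85×0.05 + 0.15×0.30) = 0.0425/0.0875 = 0.49.
- Dividing each count by its resection rate restores the truth: sensitivity = (0.255/0.30)/(0.255/0.30 + 0.0075/0.05) = 0.85/(0.85 + 0.15) = 0.85, and specificity likewise.

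Precision would also be poor. If 10% of 250 were resected (25 patients, about 13 mucinous at prevalence 0.5), an observed 9/13 has an exact (Clopper-Pearson) 95% interval of about 0.39 to 0.91.

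**The case against.** The strongest defence is that histology where available, otherwise a masked panel, is a practical pre-specified design that gives every patient a reference. Masking to needle and withholding aspirate results keep the assays out of their own reference and limit board error that differs by arm. That stands, and it is why the pooled table should stay. Masking does not remove board misclassification, however, and does not separate the two references.

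Several stronger readings are tempting, and the documents do not support them:

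- *The board judges on imaging alone.* It also uses baseline medical history, including prior necrotizing pancreatitis and trauma.
- *The aspirate decides who is operated on.* The documents say only that yield may affect treatment decisions and list management as an endpoint. The link is an inference. That the board supplies most of the references is likewise likely, but not stated.
- *Pooling understates accuracy.* It does under independent errors, but correlated errors can reverse the sign.
- *Pooling creates a false difference between needles.* In the same illustration, 15% resected in one arm and 30% in another gives 0.701 against 0.30×0.85 + 0.70×0.675 = 0.728, a gap of 2.6 points. Nothing in the documents supports such a difference in resection. Sampling error is far larger: at 70% accuracy with 121 and 61 patients, 1.96×√(0.21/121 + 0.21/61) = 14 points. No between-arm test is specified for endpoint h.
- *Histology alone should be the headline.* Step 5 of the working shows that it can mislead more than the pooled table.

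**Conclusion.** The concern holds as a reporting gap. The only planned accuracy analysis merges a reference the plan calls the gold standard with one it calls a surrogate, and nothing elsewhere in the protocol or SAP separates them. That rests on the text and the formulas alone.

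The size and direction of the resulting bias cannot be derived from the documents. Under the stated assumptions, a true 85% reads anywhere from about 64% to 82% with independent errors (board accuracy 65% to 95%), and about 89% with fully shared errors at board accuracy 75%. These are illustrations, not estimates for this trial.

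The scope is secondary endpoint h and, through it, the diagnostic-accuracy part of the primary objective. A reader might infer that the primary endpoint, endpoint c or the sample size is in doubt. They are not: neither powered endpoint uses the reference diagnosis.

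**What to change.** In SAP 5.1.2, with matching text in Protocol Appendix C.3:

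1. Keep the pooled 5x5 table and its measures.
2. Add the same table and every accuracy measure separately for histology-verified and board-verified subjects, with counts by arm and exact confidence intervals.
3. Label the board-verified result as agreement with the history-and-imaging consensus diagnosis, not as accuracy.
4. Do not present the histology-verified result as the unbiased headline. Report the 30-day resection rate by aspirate result, and give the histology result either a partial-verification caveat or a correction that weights by those rates. State the correction's assumption that, given the aspirate result, resection does not depend further on the true disease state.

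The cost is SAP wording and extra tables. The split needs only the reference source, which the plan's own rule determines for each subject. The downside is that few patients are likely to be resected within 30 days, so the histology-only estimate will be imprecise and drawn from a selected group, and the weighting will be unstable if very few assay-negative patients are resected.
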